## 3 Study Endpoints

Timeframe to endpoints: After the 3 month treatment period, the endpoints will be assessed for 12 months

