### 3.2 Secondary Endpoints

- Total number of cardiovascular hospitalizations during the trial period for each group
- Time to Recurrence of AF lasting longer than 30 seconds
- Change in distance walked in 6-minute walk test
- Change in the Rand 36-Item Health Survey (SF-36) during trial period
- Change in EF during trial period

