## 6 Study Procedures

The time course for the trial is divided into a treatment period followed by the trial period. The treatment period will include the first 3 months post enrollment or post procedure during which repeat ablation can be performed and titration of AAD dosages can be performed. The follow-up trial period will commence at end of treatment period and all outcome data will be collected over a 12 month period.

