### 6.4.2 12-15 Month Post Randomization Visit (+/- 3 weeks)

1. Record data from office visit if completed as standard of care
2. Record vital signs (HR/BP)
3. Record use of select medications
4. Record 12 lead ECG
5. Record Echocardiogram
6. Perform 6-minute walk test
7. Collect Rand 36-Item Health Survey (SF-36)
8. Collect Atrial Fibrillation severity Scale (AFSS)
9. Assessment of NYHA class
10. Record the data from remote arrhythmia monitoring and /or ECGs completed as a part of standard of care
11. Record the results from routine lab assessment and clinical indicated tests completed as a part of Standard of care: these may include but not limited to:
  - Blood tests, chest x-rays, pulmonary function test, Spiral CT to assess pulmonary vein stenosis (only if in the ablation arm only if clinically indicated )
12. Assessment of Adverse Events (AE) and Serious Adverse Events (SAE)
13. Record any hospitalizations including short stays and hospital admissions.

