## 7 Statistical Analysis

A Cox proportional hazards regression model adjusting for site and randomization strata will be used to test for treatment group differences in the primary endpoint. Kaplan-Meier estimates and curves will also be created. Secondary endpoints will be analyzed using a two-sample t-test or Wilcoxon signed rank as appropriate. Depending on the distribution for the total number of hospitalizations it will be treated as a continuous variable or collapsed into categories (0-2, 3-5, 5-7, >7). The intent-to-treat population will be used for all analysis. Patients who drop-out before study completion due to cardiac causes will be considered as having an event at the time drop-out for the primary analysis. Patients who drop-out for other reasons will be treated as censored observations at the time of drop-out in the primary analysis. Analysis based on the protocol and safety populations will also be done. All statistical tests will be two-sided and an alpha of 0.05 or less will be considered statistically significant. Mean and

CONFIDENTIAL

This document is confidential and the property of The Cleveland Clinic Foundation. No part of it may be transmitted, reproduced, published, or used by other persons without prior written authorization from the study sponsor.

V6.0\_22May2017

standard deviation or frequency and percent will be used to describe demographics, medical history and other baseline variables by treatment group. T-tests or chi-square tests as appropriate will be used to compare the baseline factors by treatment group.

Sample size is based on an expected 30-40% rate of hospitalization for recurrence of AF, heart failure or DC conversion at 12 months in the ablation arm and a 60% rate at 12 months in the AAD arm. One hundred patients per treatment arm are needed to have 80% power at an alpha level of 0.05 to detect this difference. Assuming a 10% drop-out rate, a total of 220 patients will need to be enrolled. Randomization will be 1:1 based on EF stratification EF  $\leq$ 35% and >35%.

**Safety population:** All patients that received any ablation treatment **or at least 1 dose of AAD** will be included in the safety population.

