## 7.1 Subject Population for Analysis

Analysis populations are defined as following:

**Intent-to-treat population (ITT):** All patients that are randomized to either the ablation treatment or antiarrhythmic treatment are included in the intention to treat population. ITT population is analyzed based on the treatments they are randomized to.

**Per-protocol population:** Patients that satisfy all the inclusion and exclusion criteria, and receive and stay within the randomized treatment during the treatment period are included in the per-protocol. The per-protocol population is analyzed based on the actual treatment they receive.

**Safety population:** All patients that received any ablation treatment **or at least 1 dose of AAD** will be included in the safety population.

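### Time to AF recurrence, a secondary endpoint, has no survival test and no censoring rule; the tests named are a t-test, which cannot use censored times, and a signed-rank test, which is paired

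*Combined protocol and SAP*

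**What the plan says.** - Section 3.2 and the synopsis list as a secondary endpoint "Time to Recurrence of AF lasting longer than 30 seconds". AF recurrence is also named in the hypothesis in Section 2.1.
- Section 7 covers the secondary endpoints as a class: "Secondary endpoints will be analyzed using a two-sample t-test or Wilcoxon signed rank as appropriate". Only the hospitalization count gets handling of its own.
- The Cox model "will be used to test for treatment group differences in the primary endpoint". The synopsis ties it to the primary endpoint too. The Kaplan-Meier sentence that follows names no endpoint and no test.
- Both drop-out rules are limited to the primary analysis. Cardiac drop-outs count as events there. For the rest: "Patients who drop-out for other reasons will be treated as censored observations at the time of drop-out in the primary analysis".
- Section 7.1 defines the ITT set: "All patients that are randomized to either the ablation treatment or antiarrhythmic treatment are included in the intention to treat population". It does not say what time a patient without recurrence contributes.
- Section 3 says that after the treatment period "the endpoints will be assessed for 12 months". Section 6.4.2 places the last visit 12 to 15 months after randomization, plus or minus 3 weeks.
- Section 6 defines the time course: "The treatment period will include the first 3 months post enrollment or post procedure". Section 6.1, writing of primary outcome data in the ablation arm, ends that period three months after randomization.

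**The concern.** Time to recurrence is a censored outcome. By the synopsis rates, 60-70% of the ablation arm and 40% of the AAD arm are still free of AF at month 12, before any drop-out. The plan raises three difficulties.

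1. The signed-rank test needs paired or one-sample data. Between two randomized arms there are no pairs.
2. A t-test, or a corrected rank-sum test, treats each recorded time as a recurrence time or omits the patient. The plan does not say which applies to a patient who leaves early without recurrence. Entering the last time makes leaving look like recurring; if one arm loses more patients, that shifts the comparison even when the treatments are equal.
3. The point from which time is counted is not settled, because Sections 6 and 6.1 describe the end of the treatment period differently.

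At stake are the power and, if drop-out is unequal, the type I error of an endpoint named in the hypothesis. The trial is unblinded, which is a further reason to fix the method before analysis.

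**Working it through.** **The plan's own figure.** Inputs (synopsis and Section 7): 40% versus 60% at 12 months, two-sided alpha 0.05, 80% power. For two proportions with pooled null variance:

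n = [1.960 × √(2 × 0.5 × 0.5) + 0.842 × √(0.4 × 0.6 + 0.6 × 0.4)]² / 0.20² = (1.386 + 0.583)² / 0.04 ≈ 97 per arm.

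The plan states 100, at which power is 81.2%. Its total of 220 is 200 × 1.10; 200 / 0.90 gives 223. The sample size therefore reproduces, and nothing below changes it. At 30% versus 60%, 42 per arm would suffice, so 100 fits the 40% end of the range.

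**Simulation of this endpoint.** Assumptions, since the documents do not give them:
- Recurrence times are exponential with monthly hazard −ln(1 − p)/12. For p = 0.40 this is 0.511/12 = 0.0426; for p = 0.60 it is 0.916/12 = 0.0764. The hazard ratio is 0.557.
- Follow-up ends at month 12 of the trial period.
- A drop-out leaves at a time uniform over 0-12 months, independent of recurrence.
- Log-rank stands in for the Cox test without covariates.
- There are 15,000 trials per scenario (10,000 for the visit-window case). The Monte Carlo standard error at a 5% rate is √(0.05 × 0.95 / 15,000) ≈ 0.2 points.

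Handling A keeps drop-outs and enters their last time as a recurrence time. Handling B sets drop-outs without recurrence to missing. Event-free completers keep their last time in both.

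Rejection rates in %; drop-out is ablation/AAD in the power rows:

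| Recurrence; drop-out | n per arm | Log-rank | t-test A / B | Rank-sum A / B |
|---|---|---|---|---|
| 40 v 60; none | 100 | 82.5 | 75.3 | 80.9 |
| 30 v 60; none | 100 | 99.3 | 98.1 | 99.3 |
| 40 v 60; 10/10 | 110 | 85.1 | 72.4 / 77.0 | 77.9 / 82.4 |
| 30 v 60; 10/10 | 110 | 99.4 | 96.4 / 98.1 | 98.0 / 99.2 |
| 40 v 60; 15/5 (assumed) | 110 | 85.1 | 46.3 / 67.8 | 50.7 / 74.1 |
| 50 v 50; 10/10 | 110 | 5.0 | 5.0 / 5.2 | 5.1 / 5.2 |
| 50 v 50; 8/12 (assumed) | 110 | 5.1 | 5.5 / 5.0 | 5.9 / 5.0 |
| 50 v 50; 5/15 (assumed) | 110 | 5.1 | 10.3 / 6.2 | 10.8 / 6.0 |

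**Last-visit timing.** If the trial period starts at month 3, a last visit at month 12 to 15 falls 12 − 3 = 9 to 15 − 3 = 12 months into it. With last visits assumed uniform over that range in both arms, no drop-out, 100 per arm, 40% versus 60%, and event-free completers entered at their last-visit time, power is 79.4% log-rank, 70.4% t-test and 68.3% rank-sum. Under the null with the same window and 10% drop-out in each arm (110 per arm), all rejection rates are 4.7-5.1%.

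**Sensitivity.** With exponential drop-out times (10,000 trials, 110 per arm, 10% drop-out in each arm, 40% versus 60%), power is 84.6% log-rank, 71.9% t-test A and 77.1% rank-sum A. About 52% of patients are then censored. If only patients with a recurrence were analysed, t-test power would be 8.8%. With 60% recurrence in both arms and drop-out of 15% versus 5%, type I error is 4.6% log-rank, 8.9% t-test A and 9.3% rank-sum A.

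**The case against.** The strongest reply is that one generic sentence covers five secondary endpoints. Three of them (walk distance, SF-36, EF) are changes for which a t-test is natural. The qualifier *as appropriate* and the unassigned Kaplan-Meier sentence might be read as leaving room for a survival analysis. But the qualifier chooses between the two named tests, Kaplan-Meier estimates are not a test, and nothing gives a censoring rule for this endpoint.

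On size, the reply has more force. The documents give only 10% drop-out overall. With equal drop-out, type I error holds, and rank-sum with drop-outs set to missing loses about 3 points (82% against 85%). At 30% versus 60% no method loses more than about 3 points. The 10-11% type I error and the 46% power need an assumed threefold imbalance and the less favourable handling; an 8% versus 12% split gives at most about 6%. These points stand.

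The visit-window case is also an assumption. Sections 3 and 6 intend 12 months of outcome data, and log-rank power falls there too, so part of the loss is shorter follow-up. Still, Section 6.4.2 permits such a visit and no later contact is named.

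The time-origin conflict bears first on the primary endpoint and does not by itself support the point about tests. It matters here only because a survival analysis needs a stated origin. Finally, a log-rank test with a censoring rule would also close the gap; the adjusted Cox model is preferred because it mirrors the primary analysis.

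**Conclusion.** The concern holds and should be fixed before analysis. It rests on the text: the tests assigned to this endpoint are a paired test that does not fit the design and a t-test with no place for censored times, and no rule says how patients without recurrence are handled.

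The size is moderate and conditional. With complete 12-month follow-up, rank-sum is valid and close to log-rank (81% against 82%), and the t-test gives 75%. With 10% drop-out in each arm at 40% versus 60%, the loss against log-rank is about 8-13 points for the t-test and 3-7 for rank-sum. Inflated type I error requires unequal drop-out, for which the documents give no figures. Log-rank stays near 5% because drop-out is assumed unrelated to recurrence; drop-out for cardiac causes may not be. The primary analysis and sample size are not affected.

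**What to change.** In Section 7:

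1. Analyse time to AF recurrence with a Cox model adjusted for site and EF stratum, with Kaplan-Meier curves.
2. Count time from one stated origin, after reconciling Sections 6 and 6.1 on when the treatment period ends.
3. Censor patients without recurrence at their last rhythm assessment or at month 12 of the trial period, whichever comes first.
4. State how drop-out for cardiac causes and death without recurrence are handled for this endpoint.
5. Replace the signed-rank test with the Wilcoxon rank-sum test for the other between-arm secondary comparisons.

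The cost is a few sentences and a little more analysis work. Sections 6.4.1 and 6.4.2 take rhythm data from routine care, so the date of the last rhythm assessment may vary and must be available for every patient. Design, visits and sample size stay as they are.

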## 6.4 Follow Up (Month 3 through Month 15)

### 6.4.1 3-6 Months Post Randomization Visit (+/- 3 weeks)

1. Record data from office visit if completed as standard of care
2. Record vital signs (HR/BP)
3. Record use of select medications
4. Record 12 lead ECG results
5. Perform 6-minute walk test
6. Collect Rand 36-Item Health Survey (SF-36)
7. Collect Atrial Fibrillation Severity Scale (AFSS)
8. Assessment of NYHA class
9. Record the data from remote arrhythmia monitoring and /or ECGs completed as a part of standard of care
10. Record the results from routine lab assessment and clinically indicated tests completed as a part of Standard of care: these may include but not limited to:
  - Blood tests, chest x-rays, pulmonary function test, Spiral CT to assess pulmonary vein stenosis (only if in the ablation arm)
11. Assessment of Adverse Events (AE) and Serious Adverse Events (SAE)
12. Record any hospitalizations including short stays and hospital admissions.

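### Intent-to-treat is stated for all analyses, but no method is given for missing change scores in 6-minute walk, SF-36 and EF

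*Combined protocol and SAP*

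**What the plan says.** Section 7 handles drop-out in two sentences. Patients who leave "due to cardiac causes will be considered as having an event at the time drop-out for the primary analysis". For the rest: "Patients who drop-out for other reasons will be treated as censored observations at the time of drop-out in the primary analysis". Both rules stop at the primary analysis.

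For the secondary endpoints, section 7 names a test and nothing more: "Secondary endpoints will be analyzed using a two-sample t-test or Wilcoxon signed rank as appropriate". It also says "The intent-to-treat population will be used for all analysis", and section 7.1 puts every randomized patient in that population, adding "ITT population is analyzed based on the treatments they are randomized to". Neither section gives imputation, a repeated-measures model, a rule for death or cardiac withdrawal, or a missing-data sensitivity analysis for these endpoints.

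Section 3.2 lists five secondary endpoints, of which three are change scores: 6-minute walk, SF-36 and EF. The walk endpoint, "Change in distance walked in 6-minute walk test", names no comparison visit. SF-36 and EF change are tied to the trial period, which sections 3 and 6 start after the treatment period.

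The Study Assessments table and sections 6.3, 6.4.1 and 6.4.2 schedule walk and SF-36 at baseline, 3-6 months ("Perform 6-minute walk test") and 12-15 months. Echocardiography is scheduled at baseline and 12-15 months only. No visit is scheduled at withdrawal.

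**The concern.** A two-sample test on a change score needs both values. With no rule for a missing final value, the test runs on whoever attended the last visit. The plan regards leaving for a cardiac reason as informative enough to count as a failure in the primary analysis, yet the same patients would contribute nothing to a comparison of final walk distance, SF-36 or EF.

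Patients who leave because they are getting worse are likely to have the poorest values. If one arm loses more of them, its remaining patients look better than the arm as randomized. The trial is unblinded, so unequal losses cannot be ruled out. Three of the five secondary endpoints are exposed. If the handling is left open, it will be chosen after the pattern of losses is known.

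**Working it through.** **1. The plan's own figure (section 7).** Inputs: 40% (upper end of the 30-40% range) against 60%, two-sided alpha 0.05, 80% power.

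n per arm = [1.960 x sqrt(2 x 0.5 x 0.5) + 0.842 x sqrt(0.4 x 0.6 + 0.6 x 0.4)]^2 / 0.20^2 = 96.9, so 97, against the stated 100. Power at 100 per arm is 81.2%. Drop-out: 200 x 1.10 = 220 as stated (200 / 0.90 gives 223). The sample size reproduces. It concerns the primary endpoint, and its 10% is a single overall allowance, not split by arm or cause.

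**2. What is measured, and what rule applies.**

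| Endpoint | Baseline | 3-6 months | 12-15 months | Rule if the final value is missing |
|---|---|---|---|---|
| Primary (time to event) | - | - | - | Event if cardiac drop-out, otherwise censored |
| 6-minute walk | yes | yes | yes | none stated |
| SF-36 | yes | yes | yes | none stated |
| EF | yes | not scheduled | yes | none stated |

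Take a patient who leaves at month 8 for a cardiac reason. In the primary analysis this is an event at month 8. For EF there is no scheduled post-baseline value, so no change score. For walk and SF-36 there should be a 3-6 month value, but the plan does not say whether it is used.

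**3. Loss of precision.** 220 x 0.90 = 198, or 99 per arm if balanced. Detectable difference at 80% power = (1.960 + 0.842) x sqrt(2/n): 0.378 SD at 110 per arm, 0.398 SD at 99. This is small; the issue is bias.

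**4. Bias.** Let arms A and B lose fractions a and b, and let leavers' unobserved change be D worse than that of patients who stay. An arm's all-randomized mean is its observed mean minus (loss fraction x D). So:

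observed difference minus all-randomized difference = (b - a) x D, in favour of the arm with more losses.

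The documents give neither a and b nor D. The values below are assumptions, for illustration only.

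- In metres, at 5% and 15% loss: 0.10 x 30 = 3 m; 0.10 x 100 = 10 m.
- At 10% in both arms with the same D: 0.

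In SD units, with 110 randomized per arm, D = 0.5 to 1.0 SD and se = sqrt(1/n1 + 1/n2), the two-sided type I error is Phi(-1.96 + bias/se) + Phi(-1.96 - bias/se):

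| Loss by arm | Bias (SD) | Type I error |
|---|---|---|
| 10% / 10% | 0 | 5% |
| 5% / 15% | 0.05-0.10 | 6.4%-10.8% |
| 0% / 20% | 0.10-0.20 | 10.8%-28.8% |

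**The case against.** The strongest reply is that silence is not a decision to analyse completers. Several stronger readings are tempting, and the documents do not support them.

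- *The plan tests completers only and so breaches ITT.* It never says so. ITT in section 7.1 concerns who belongs to the population and by which arm they are analysed, and a missing value does not breach that. What is missing is a method for carrying it out on these endpoints.
- *The 3-6 month walk and SF-36 values are thrown away.* Their use is unspecified. Because the trial period starts after the treatment period, the 3-6 month SF-36 could even be read as the starting point of the change.
- *A patient leaving at month 8 can have no later EF.* There is no scheduled echocardiogram, but section 6.4.1 records clinically indicated tests from an open list, so one might be captured.
- *The comparison will flatter the drug arm, since it is expected to have 60% events against 30-40%.* Events are not drop-outs, and the plan does not say how many patients leave after one.

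It is also fair that no walk SD or important difference is given, so 3-10 m cannot be judged large or small, and that the 10% is a sample-size allowance rather than a forecast of missing walk tests.

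These replies limit the wording and the size. They do not supply the missing rule. With only a two-sample test specified, a comparison of change to the final visit leaves out patients without that value. For EF there is no other scheduled value to fall back on.

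**Conclusion.** The point holds as a gap between the stated population and the stated methods. Section 7 claims ITT for all analyses, confines its drop-out rules to the primary analysis, and offers only a two-sample test for three change scores. As written, a test on change to 12-15 months would omit cardiac drop-outs whom the plan elsewhere counts as failures. The gap is clearest for EF; for walk and SF-36 it depends partly on an unstated choice of visit.

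Bias arises only if losses, or the deficits of those lost, differ by arm. Neither its size nor its direction follows from the documents, and every figure in metres or SD above rests on assumed loss rates and deficits. The primary endpoint and the 220-patient sample size are not affected. The change should be made before analysis, but it does not threaten the trial's main conclusion.

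**What to change.** In section 7:

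1. Define change for walk, SF-36 and EF as change from the pre-treatment baseline. For EF no other scheduled starting value exists.
2. Analyse walk and SF-36 with a mixed model for repeated measures on the baseline, 3-6 month and 12-15 month values of all randomized patients, by assigned arm, reporting the arm difference at 12-15 months. Patients who leave after the 3-6 month visit then contribute.
3. For walk, SF-36 and EF, add a rank-sum sensitivity analysis with deaths and cardiac drop-outs ranked worst, using the same cardiac drop-out classification as the primary analysis.

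For EF the main comparison still rests on patients with a final echocardiogram, and the report should say so; item 3 is its check.

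Cost: revised text in section 7 and a few extra analyses of data already scheduled. The mixed model assumes data are missing at random. The worst-rank analysis does not, but it depends on judging what is a cardiac drop-out, a term section 7 does not define, in an unblinded trial. It should therefore stay a sensitivity analysis.

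Optional: for patients who agree, carry out the final-visit assessments at withdrawal. This alters the Study Assessments table and section 6.4, so it needs a protocol change and a rule for placing an off-schedule value in the model.

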Statistical Methodology	Sample size is based on an expected 30-40% AF recurrence rate at 12 months in the ablation arm and a 60% AF recurrence rate at 12 months in the AADs. One hundred patients per treatment arm are needed to have 80% power at an alpha level of 0.05 to detect this difference. Assuming a 10% drop-out rate, a total of 220 patients will need to be enrolled. Randomization will be 1:1 based on EF stratification EF $\leq$ 35% and >35%. A Cox proportional hazards regression model adjusting for site and EF strata will be used to test for treatment group differences in the primary endpoint.

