## 2 Study Objectives

### 2.1 Objectives

- To determine if catheter-based atrial fibrillation (AF) ablation is superior to medical treatment in patients with impaired left ventricular function that has been diagnosed with symptomatic AF within the past 12 months.
- Hypothesis: In patients with an early diagnosis of AF, ablation is better than medical therapy for patients with symptomatic AF and impaired LV function in terms of recurrent and total number of hospitalizations, recurrence of AF, EF, quality of life, and 6-minute walk distance.

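### Total cardiovascular hospitalizations: a count of 5 falls in two categories, no test is assigned to the categories, and the rank test named is a paired one

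*Combined protocol and SAP*

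**What the plan says.** Section 3.2 lists this endpoint first among the secondary endpoints: "Total number of cardiovascular hospitalizations during the trial period for each group". The hypothesis in section 2.1 also rests on it, claiming benefit "in terms of recurrent and total number of hospitalizations". Section 3 fixes the window: "After the 3 month treatment period, the endpoints will be assessed for 12 months".

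The analysis is in section 7. The general rule is "Secondary endpoints will be analyzed using a two-sample t-test or Wilcoxon signed rank as appropriate". For the hospitalization total the next sentence adds that, according to its distribution, "it will be treated as a continuous variable or collapsed into categories (0-2, 3-5, 5-7, >7". The only test for categorical data that section 7 names is for baseline comparisons: "T-tests or chi-square tests as appropriate will be used to compare the baseline factors by treatment group". Section 5.4 describes 1:1 randomization stratified by EF, which gives two independent arms and no matched pairs.

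Section 7 writes only of hospitalizations in total, while section 3.2 restricts them to cardiovascular ones. I read these as the same endpoint.

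**The concern.** Three things are wrong on the face of section 7. The second and third categories share the value 5. Nothing says how the categorized count would be tested. The rank test on offer needs pairs, and the design has none.

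Two further features weaken the plan without being errors of the same kind. The lowest category puts patients with no admission together with those who had one or two, so the contrast between none and some is lost. The switch between count and categories also depends on the observed distribution, with no criterion, no timing, and no statement that the distribution is pooled over arms or viewed blind. Section 4 describes the trial as unblinded.

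At stake is the power of a secondary endpoint named in the hypothesis and, if the open choice were used badly, some excess of false positives on it.

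**Working it through.** **1. The plan's own figure.** Section 7 states 100 per arm for 40% versus 60%, two-sided alpha 0.05, 80% power. For two proportions:

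n = [1.96 × √(2 × 0.5 × 0.5) + 0.8416 × √(0.4 × 0.6 + 0.6 × 0.4)]² / 0.2² = (1.386 + 0.583)² / 0.04 = 96.9, so 97.

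This agrees with 100, and power at 100 per arm is 81.2%. The calculation does not use the hospitalization count, so nothing below changes it.

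**2. The categories.** Counts 0, 1 and 2 go to 0-2; 3 and 4 to 3-5; 6 and 7 to 5-7; 8 and above to >7. A count of 5 goes to both 3-5 and 5-7. Every other count has one place.

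**3. The rank test.** The signed rank test works on differences within pairs. A count of admissions in the trial period has no baseline value to subtract, and patients in the two arms are not paired.

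**4. Inputs for power (assumption).** The documents give no admission rate for this endpoint. I borrow 60% and 40% as the proportions with any admission. Section 7 describes the ablation figure as an "expected 30-40% rate of hospitalization for recurrence of AF, heart failure or DC conversion at 12 months in the ablation arm"; the synopsis, under Statistical Methodology, calls the same figure an "expected 30-40% AF recurrence rate at 12 months in the ablation arm". It is therefore only a rough anchor.

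- Poisson means: −ln(1 − 0.6) = 0.916 and −ln(1 − 0.4) = 0.511; rate ratio 0.511/0.916 = 0.56.
- Share with 0-2 admissions, e^(−m) × (1 + m + m²/2): AAD 0.4 × 2.336 = 93%; ablation 0.6 × 1.641 = 98%.
- With overdispersion a, P(0) = (1 + a × m)^(−1/a). Holding the means, the share with any admission becomes 53/37%, 48/34% and 41/30% at a = 0.5, 1 and 2.
- Holding 60/40 instead, m = [(1 − p)^(−a) − 1]/a gives means 1.16/0.58, 1.50/0.67 and 2.63/0.89, with rate ratios 0.50, 0.44 and 0.34.

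Both anchors are shown because neither is uniquely right.

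**5. Power.** Simulated at 100 per arm, two-sided 0.05, with 5 placed in 3-5. Chi-square is my choice, since the plan names no test for the categories.

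| Overdispersion | Means held: chi-square on categories | Means held: t-test on count | 60/40 held: chi-square on categories | 60/40 held: t-test on count |
|---|---|---|---|---|
| 0 (Poisson) | 42% | 92% | 42% | 92% |
| 0.5 | 44% | 85% | 65% | 96% |
| 1 | 33% | 73% | 77% | 98% |
| 2 | 24% | 58% | 94% | 99% |

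When admissions are common the gap can close: at an AAD mean of 2.5 and rate ratio 0.56, Poisson, it is 99% versus 100%. With overdispersion 2 at that mean it is 45% versus 70%.

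**6. Separating the categories from the choice of test.** With a rank-sum test on both scales and the means held, power on the categories versus the count is 42% vs 90%, 51% vs 78%, 50% vs 64% and 43% vs 47% at overdispersion 0, 0.5, 1 and 2. At the high end most of the gap in step 5 therefore comes from the test. With 60/40 held and overdispersion 2, the rank-sum test does as well on the categories (98%) as on the count (97%).

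**7. The overlap alone.** Moving 5 from 3-5 to 5-7 changes chi-square power by about 1 to 6 points with the means held. Only 0.2% to 1.7% of AAD patients would have exactly 5 admissions.

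**8. False positives.** If the route were chosen by a fixed rule on the pooled distribution (illustrated by a skewness cut), simulated error was 2-5%. If both routes were run and the smaller p-value kept, it was about 6-8%.

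**The case against.** The strongest reply is that this is a slip of wording on one secondary endpoint. The overlap may be a misprint for 6-7, a usable t-test already stands in the plan, and merging 0 to 2 is a design choice. The signed rank test could also suit within-patient change in EF or walk distance. Much of this stands. But the documents do not say that 6-7 was meant, no other section repairs the categories or assigns them a test, and the within-patient reading is not available for a count that starts at zero after the treatment period.

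A second reply is that the size of the loss depends on the assumed rates and on the test. That is correct. A reader might infer from the Poisson case that a real difference will usually be missed. The documents do not support that: they give no rate, and under the 60/40 anchor with overdispersion chi-square reaches 65-94%.

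A reader might also take the open choice as proof of inflated error, or as harmless. Neither follows. The text is silent on whether the distribution is pooled or blinded, and the result depends on how the choice is made.

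**Conclusion.** The point stands as an error in the written plan for one secondary endpoint and should be corrected. The overlap at 5, the missing test and the paired rank test follow from the text alone and need no assumption.

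The power loss is conditional. It is large if admissions are few and close to Poisson (about 42% versus 92%). It is smaller, though not always negligible, in the other cases shown, and part of it reflects chi-square ignoring the order of the categories. The excess of false positives, to about 6-8% from 5%, arises only if both routes are tried and the better one kept; nothing in the documents says this is intended.

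The primary Cox analysis and the sample size are unaffected. It would also go too far to say that the endpoint has no valid analysis, since the t-test on the count is one.

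**What to change.** In section 7, remove the categories as a basis for inference and name one two-sample comparison of the cardiovascular hospitalization count in advance. The t-test already in the plan will do, with counts described as 0, 1, 2, and 3 or more. Change Wilcoxon signed rank to Wilcoxon rank-sum for between-arm comparisons.

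An optional alternative is negative binomial regression with treatment, EF stratum and log time at risk as offset. It gives a rate ratio and allows for unequal follow-up, provided that leaving the study is uninformative. It brings no real power gain: with the means held it had 93%, 84%, 76% and 58% at overdispersion 0, 0.5, 1 and 2, against 93%, 83%, 74% and 59% for the t-test in a matching set of runs. Its simulated null error reached about 6%. If it is chosen, the SAP should say whether site enters, as it does in the primary model.

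The cost is a few lines of SAP text and no new data, since sections 6.4.1 and 6.4.2 already record hospitalizations. As a separate point, the synopsis, section 6 and section 6.1 differ on when the treatment period ends and the trial period starts. They should be reconciled, because that affects every endpoint.
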